The EMBER Trial for Weight Management Engagement

NCT05424081

July 1, 2021

Title : The EMBER Trial for Weight Management Engagement
Approval Period: **Draft**

Modification Form	3
Personnel Info	3
Participant Population	4
Study Location	5
General Checklist	5
Funding	7
Resources	8
Expedited Category	10
Purpose	11
Radioisotopes or Radiation Machines	17
Drugs, Reagents, Chemicals, Devices	17
Medical Equipment for Human Subjects and Laboratory Animals	18
Participant Population(a-g)	18
Participant Population(h-m)	19
Risks(a-d)	20
Privacy And Confidentiality	22
Conflict Of Interest	25
Consent Background	25
Assent Background	28
Hipaa	28
Attachments	29

Title : The EMBER Trial for Weight Management Engagement
Approval Period: **Draft**

Obligations 30

Title : The EMBER Trial for Weight Management Engagement

Approval Period: Draft

Modification

1. Summarize your proposed changes.

As previously discussed, we would like to amend this protocol to extend to the funded trial, which has the same goal and almost all of the same methods as the pilot. Therefore, we are also requesting to change the title of the IRB proposal to the title of the new grant. The two largest changes are to add a site (Houston VA Medical Center) and to have outside assessors complete follow-up assessments to ensure study staff remain blinded to participant randomization.

We have a waiver of using the VA central IRB and a single IRB waiver under review. We will not recruit Houston participants until we have/upload an approval letter from their IRB. We will not transfer data to/from the outside assessor until all procedures are approved by VA ISOs, ACOS, and other necessary parties.

2. Indicate Level of Risk

No Change

3. Update the Conflict of Interest (COI) section if any changes in COI have been made since the last protocol submission.

N Is there a change in the conflicting interest status for any existing personnel on this protocol?

Protocol Director

Name [name]		Degree (Program/year if student) PhD		Position, e.g. Assistant Professor, Resident, etc. Clinical Assistant Professor (Affiliated) [VAPAHCS]
Department Psych/General Psychiatry and Psychology (Adult)	5722	[contact][name]		E-mail [contact]
CITI Training current				Y

Admin Contact

Name [name]		Degree (Program/year if student) BA		Position, e.g. Assistant Professor, Resident, etc. RA
Department		[contact]		E-mail [contact]
CITI Training current				Y

Investigator

- Is Stanford the coordinating institution or are you the lead investigator for this multi-site study? Y

Site Name	Contact Name	Contact Phone	Contact Email	Permission?	Engaged?
Houston VAMC	[name]	[contact]	[contact]	N	Y

Collaborating Institution(s)

Yes/No

- Are there any collaborating institution(s)? A collaborating institution is generally an N

Title : The EMBER Trial for Weight Management Engagement

Approval Period: Draft

institution that collaborates equally on a research endeavor with one or more institutions.

Cancer Institute

Yes/No

- Cancer-Related Studies (studies with cancer endpoints), Cancer Subjects (e.g., clinical trials, behavior/prevention) or Cancer Specimens (e.g., blood, tissue, cells, body fluids with a scientific hypothesis stated in the protocol).

N

Clinical Trials

Yes/No

- Investigational drugs, biologics, reagents, or chemicals? N
- Commercially available drugs, reagents, or other chemicals administered to subjects (even if they are not being studied)? N
- Investigational Device / Commercial Device used off-label? N
- IDE Exempt Device (Commercial Device used according to label, Investigational In Vitro Device or Assay, or Consumer Preference/Modifications/Combinations of Approved Devices) N
- Will this study be registered on# clinicaltrials.gov? (See Stanford decision tree) Y
- Is Stanford responsible for ClinicalTrials.gov registration? (See Stanford decision tree) NCT# N

Tissues and Specimens

Yes/No

- Human blood, cells, tissues, or body fluids (tissues)? N
- Tissues to be stored for future research projects? N
- Tissues to be sent out of this institution as part of a research agreement? For guidelines, please see <https://sites.stanford.edu/ico/mtas> N

Biosafety (APB)

Yes/No

- Are you submitting a Human Gene Transfer investigation using a biological agent or recombinant DNA vector? Please review the Administrative Panel on BioSafety website form more information. N
- Are you submitting a Human study using biohazardous/infectious agents? If yes, refer to the Administrative Panel on BioSafety website prior to performing studies. N
- Are you submitting a Human study using samples from subjects that are known or likely to contain biohazardous/infectious agents? If yes, refer to the Administrative Panel on BioSafety website prior to performing studies. N

Human Embryos or Stem Cells

Yes/No

- Human Embryos or Gametes? N

Title : The EMBER Trial for Weight Management Engagement

Approval Period: Draft

- Human Stem Cells (including hESC, iPSC, cancer stem cells, progenitor cells) N

Veterans Affairs (VA)

Yes/No

- The research recruits participants at the Veterans Affairs Palo Alto Health Care System(VAPAHCS). Y
- The research involves the use of VAPAHCS non-public information to identify or contact human research participants or prospective subjects or to use such data for research purposes. Y
- The research is sponsored (i.e., funded) by VAPAHCS. N
- The research is conducted by or under the direction of any employee or agent of VAPAHCS (full-time, part-time, intermittent, consultant, without compensation (WOC), on-station fee-basis, on-station contract, or on-station sharing agreement basis) in connection with her/his VAPAHCS responsibilities. Y
- The research is conducted using any property or facility of VAPAHCS. Y

Equipment

Yes/No

- Use of Patient related equipment? If Yes, equipment must meet the standards established by Hospital Instrumentation and Electrical Safety Committee [contact]) N
- Medical equipment used for human patients/subjects also used on animals? N
- Radioisotopes/radiation-producing machines, even if standard of care? N
http://www.stanford.edu/dept/EHS/prod/researchlab/radlaser/Human_use_guide.pdf More Info

Payment

Yes/No

- Subjects will be paid/reimbursed for participation? See payment considerations. Y

Funding

Yes/No

- Training Grant? N
- Program Project Grant? N
- Federally Sponsored Project? Y
- <https://doresearch.stanford.edu/policies/research-policy-handbook/definitions-and-types-agreements/specialized-categories-sponsored-p> Industry Sponsored Clinical Trial? N

Funding

Funding - Grants/Contracts			
Funding Administered By :	VA	SPO # (if available) :	
Grant # (if available) :	CDA15-257	Funded By (include pending) :	VA HSRD

Title : The EMBER Trial for Weight Management Engagement

Approval Period: Draft

Principal Investigator : [name]

Grant/Contract Title if different from Protocol Title :

Patient-Centered Strategies to Engage Veterans in Behavioral Health Treatments

Y For Federal projects, are contents of this protocol consistent with the Federal proposal?

N Is this a Multiple Project Protocol (MPP)?

N Is this protocol under a MPP?

Funding Administered By : VA

SPO # (if available) :

Grant # (if available) : IIR 19-422

Funded By (include pending) : VA HSR&D

Principal Investigator : [name]

Grant/Contract Title if different from Protocol Title :

Staff have completed all mandatory annual training courses(e.g., VA Privacy and Information Security Awareness and Rules of Behavior, VA Privacy and HIPAA Training, CITI Training). The PI meets personally with all study staff on an intensive basis during their first month in the position, to assure that they understand all components of their roles, including data management procedures, data security procedures, etc.

c) Facilities.

Please describe and justify.

VA Palo Alto Health Care System

The VA Palo Alto Health Care System (VAPAHCS) will serve as the main research facility; research team members are all based at VAPAHCS.

Center for Innovation to Implementation

The Center for Innovation to Implementation (Ci2i) is a VA HSR&D Center of Innovation (COIN) located at VAPAHCS. Ci2i staff include over 30 core investigators who conduct numerous forms of health services research and have expertise in administrative database analyses, implementation science, behavioral health, qualitative research, intervention design and evaluation, longitudinal analyses, and multi-level analyses.

With regards to relevant technology, Ci2i has a centralized server and mass data storage that is firewalled and encrypted. The secure system is hosted and managed by VA OIT (Office of Information technology). There are daily backups as well as monthly full system back-ups, along with other state of the art security features, such as a locked server room with alarms.

d) Sufficient time.

Explain whether you will have sufficient time to conduct and complete the research. Include how much time is required.

We anticipate that this research will take approximately 3.5 years to complete, including presentation of findings and manuscript preparation.

e) Access to target population.

Explain and justify whether you will have access to a population that will allow recruitment of the required number of participants.

We plan to recruit 470 veteran participants out of over ten thousand veterans with obesity who use the VA Palo Alto & Houston Healthcare Systems, we do not anticipate difficulty meeting recruitment goals.

f) Access to resources if needed as a consequence of the research.

State whether you have medical or psychological resources available that participants might require as

Title : The EMBER Trial for Weight Management Engagement

Approval Period: Draft

a consequence of the research when applicable. Please describe these resources.

We do not believe that participants in this minimal risk study will require medical or psychological resources. However, in the event they do, they will be referred to appropriate VA veteran health services.

g) Lead Investigator or Coordinating Institution in Multi-site Study.

Please explain (i) your role in coordinating the studies, (ii) procedures for routine communication with other sites, (iii) documentation of routine communications with other sites, (iv) planned management of communication of adverse outcomes, unexpected problems involving risk to participants or others, protocol modifications or interim findings.

Coordination with other site will be done via email, phone, and video conferencing. [name] and the research coordinator will visit Houston in Y1 to ensure site staff have adequate training and to understand the Houston clinical context. [name] (Houston Site PI) will travel to Palo Alto in Y4 to help interpret results and plan future trials. Meeting Structure: [name] will lead monthly meetings with all co-investigators (weekly with [name] during Y1-Y2), and weekly meetings with research staff. [name] will meet weekly with the study coordinator. The coordinator will meet regularly with research assistants at both sites to guide training, recruitment, and progress. [name] will meet regularly with biostatistician, [name]. Davis Research: We propose that this (or similar) company conduct blinded post assessments. Communication will include weekly calls / reports, and Stata files sent quarterly.

Adverse outcomes, unexpected problems, and/or protocol modifications will be reported to [name] immediately and reported to regulatory bodies as appropriate (e.g., IRBs, DSMB). As described elsewhere, we will complete interim analyses at n=200, with results reported to the DSMB.

Expedited Form

A protocol must be no more than minimal risk (i.e., "not greater than those ordinarily encountered in daily life") AND must only involve human subjects in one or more of the following paragraphs.

Select one or more of the following paragraphs:

1. N Clinical studies of drugs and medical devices only when condition (a) or (b) is met.

- a) Research on drugs for which an investigational new drug application (21 CFR Part 312) is not required. (Note: Research on marketed drugs that significantly increases the risks or decreases the acceptability of the risks associated with the use of the product is not eligible for expedited review.)
- b) Research on medical devices for which
 - i) an investigational device exemption application (21 CFR Part 812) is not required; or
 - ii) the medical device is cleared/approved for marketing and the medical device is being used in accordance with its cleared/approved labeling.

2. N Collection of blood samples by finger stick, heel stick, ear stick, or venipuncture as follows:

- a) from healthy, nonpregnant adults who weigh at least 110 pounds. For these subjects, the amounts drawn may not exceed 550 ml in an 8 week period and collection may not occur more frequently than 2 times per week; or
- b) from other adults and children, considering the age, weight, and health of the subjects, the collection procedure, the amount of blood to be collected, and the frequency with which it will be collected. For these subjects, the amount drawn may not exceed the lesser of 50 ml or 3 ml per kg in an 8 week period and collection may not occur more frequently than 2 times per week.

3. N Prospective collection of biological specimens for research purposes by non invasive means.

4. N Collection of data through non invasive procedures (not involving general anesthesia or sedation)

Title : The EMBER Trial for Weight Management Engagement
Approval Period: Draft

routinely employed in clinical practice, excluding procedures involving x-rays or microwaves. Where medical devices are employed, they must be cleared/approved for marketing. (Studies intended to evaluate the safety and effectiveness of the medical device are not generally eligible for expedited review, including studies of cleared medical devices for new indications.)

Examples:

- a) physical sensors that are applied either to the surface of the body or at a distance and do not involve input of significant amounts of energy into the subject or an invasion of the subject's privacy;
 - b) weighing or testing sensory acuity;
 - c) magnetic resonance imaging;
 - d) electrocardiography, electroencephalography, thermography, detection of naturally occurring radioactivity, electroretinography, ultrasound, diagnostic infrared imaging, doppler blood flow, and echocardiography;
 - e) moderate exercise, muscular strength testing, body composition assessment, and flexibility testing where appropriate given the age, weight, and health of the individual.
5. Y **Research involving materials (data, documents, records, or specimens) that have been collected, or will be collected solely for nonresearch purposes (such as medical treatment or diagnosis). (NOTE: Some research in this paragraph may be exempt from the HHS regulations for the protection of human subjects. 45 CFR 46.101(b)(4). This listing refers only to research that is not exempt.)**
 6. Y **Collection of data from voice, video, digital, or image recordings made for research purposes.**
 7. Y **Research on individual or group characteristics or behavior(including, but not limited to, research on perception, cognition, motivation, identity, language, communication, cultural beliefs or practices, and social behavior) or research employing survey, interview, oral history, focus group, program evaluation, human factors evaluation, or quality assurance methodologies. (NOTE: Some research in this category may be exempt from the HHS regulations for the protection of human subjects. 45 CFR 46.101(b)(2) and (b)(3). This listing refers only to research that is not exempt.)**

1. Purpose

- a) **In layperson's language state the purpose of the study in 3-5 sentences.**

We will test the effectiveness and collect preliminary information that may help in its future implementation of EMBER, a patient-facing, self-help tool to increase weight loss treatment engagement. In this two site study we will recruit patients (n=470) from the VA Palo Alto Health Care System (VAPAHCS) in Palo Alto, CA and the Houston VA Medical Center (VAMC) in Houston Texas.

- b) **State what the Investigator(s) hope to learn from the study. Include an assessment of the importance of this new knowledge.**

We hope to learn about the effectiveness EMBER, i.e., whether it increases weight loss treatment engagement among veterans. This information is important because many veterans have obesity and increasing weight management engagement could lead to weight loss and subsequent improvements in morbidity and quality of life.

- c) **Explain why human subjects must be used for this project. (i.e. purpose of study is to test efficacy of investigational device in individuals with specific condition; purpose of study is to examine specific behavioral traits in humans in classroom or other environment)**

Title : The EMBER Trial for Weight Management Engagement

Approval Period: Draft

Because we are testing EMBER, a tool to increase engagement in weight loss treatments, we need to include patients for whom the tool is intended.

2. Study Procedures

- a) **Please SUMMARIZE the research procedures, screening through closeout, which the human subject will undergo. Refer to sections in the protocol attached in section 16, BUT do not copy the clinical protocol. Be clear on what is to be done for research and what is part of standard of care.**

Recruitment

We will recruit participants via batched opt-out letters (see attachment), which will include the consent form, and follow-up phone calls. These participants will be identified via the VA Informatics and Computing Infrastructure (VINCI).

VINCI is a VA HSR&D resource center that provides a secure, central analytic platform for performing research and supporting clinical operations activities. It can provide us with a list of veterans who meet our inclusion/exclusion criteria.

If a VINCI programmer cannot provide us with a list, we will have another programmer create the cohort on VINCI.

We expect to send roughly 2,000 letters, based on a 10-30% response rate in prior work.

We will oversample women veterans to ensure adequate representation. In addition, we will track the race/ethnicity and age of participants. If we do not obtain adequate representation of any of the aforementioned groups, we may oversample the group(s).

We are requesting a full waiver of HIPAA for this study, to cover the access to PHI prior to screening, after screening (but before enrollment in the study), and also data collected after enrollment in the study.

Potential participants will be screened over the phone to determine whether they meet eligibility criteria. If they meet criteria via self-report, we will then use CPRS/VistAWeb to screen clinical records and confirm eligibility, if necessary, which may occur before and after mailings for participants recruited via mail.

We will inform primary care clinic directors that we are conducting this study (via email) and ask them to let us know if they have any questions or concerns.

Title : The EMBER Trial for Weight Management Engagement

Approval Period: Draft

CONSENT

Once a participant is deemed eligible and they remain interested in participating, we will complete the verbal consent process over the phone. We are requesting a waiver of documentation of consent as it would be an undue burden for participants in this minimal risk study. Veterans will be given adequate time to review the consent and ask questions before verbally giving consent over the phone. If the veteran does not have the consent sheet, it will be resent or read verbatim over the phone. We may also direct potential participants to website that displays the consent form. If the person obtaining consent believes the veteran cannot give consent, the process will be terminated.

Baseline questionnaires: After the consent process, participants will complete the following questionnaires over the phone (see section 16 attachments):

- Baseline Questionnaire (demographics, motivation, knowledge, weight management beliefs/behaviors/outcomes, and preferences)
- Screen for Disordered Eating (Maugen et al)
- Stanford Leisure-Time Activity Categorical Item (L-Cat)
- Brief Illness Perception Questionnaire (Brief-IPQ)
- VR-12 (SF-12 for Veterans)
- PHQ-9

Staff will enter participant responses directly into Qualtrics. Participants will not use Qualtrics as all assessments are completed over the phone. This method will ensure complete data entry at the time of assessment and reduce the number of paper records.

Randomization: Participants will then be randomized 1:1 to the intervention or control arm, stratified by site and gender. To conceal allocation, the randomization algorithm will allocate stratum-specific participants to arms within randomly generated block sizes.

Participants in the control arm will be provided with information about available VA Palo Alto or Houston Programs via the modality of their choice (i.e., paper or online; see attachment). Participants in the treatment arm will be provided with a link to the web version of the self-help tool (via mail and/or verbally) or mailed a paper version of EMBER, depending on their preference. All participants will receive the Participant Letter (attachment 16).

EMBER, the self-help tool: Both the paper and online versions of the self-help tool help veterans consider the pros and cons of weight loss and weight management treatments by using the decisional balance exercise that is

Title : The EMBER Trial for Weight Management Engagement

Approval Period: Draft

common in Motivational Interviewing. In addition, the tool will help veterans set a concrete goal to engage in a weight loss treatment. The tool IS NOT a weight loss treatment, instead it is meant to engage veterans in existing treatments. The paper version of the tool is attached (section 16). Treatments will be specific to those available in Palo Alto and Houston.

The online versions of the tool and control materials are hosted on Qualtrics, which is a HIPAA compliant survey website. Access to Qualtrics is provided through Stanford. Qualtrics will collect data on participants' IP addresses, answers to tool questions, and length of time on the website. See section 16 for screenshots.

10-day call: Roughly 10 days after mailing patients study materials, study staff will complete a call with participants to understand whether they used study materials and to review study materials with participants, if necessary. 10-day call guides are provided in Section 16. These calls will be audio recorded to assess fidelity.

Follow-up questionnaires: Eight weeks and 24 weeks after the tool is sent, an outside company will call participants to have them complete the following questionnaires (see attachments):

- Follow-up Questionnaire (weight loss, thoughts about tool/control materials, weight, height, motivation, self-efficacy)
- Screen for Disordered Eating (Maguen et al)
- Stanford Leisure-Time Activity Categorical Item (L-Cat)
- Brief Illness Perception Questionnaire (Brief-IPQ)
- VR-12 (SF-12 for Veterans)
- PHQ-9

Participants who we cannot be reached by phone for follow-up calls will be sent the lost to follow-up letter.

VINCI/CPRS/VISTA web-based follow-up: The primary outcome, whether participants used a weight loss treatment by 2-month follow-up. This is defined as visits in MOVE! or nutrition clinics, recreation therapy visits, Vida app use.

Using VINCI, we will also collect information on participants' height and weight at baseline, two months, and six months. We will collect information on mental and physical health diagnoses as well as hospitalizations and death (for adverse event reporting). Therefore, we are requesting an amendment of HIPAA authorization to be able to access these limited portions of

Title : The EMBER Trial for Weight Management Engagement

Approval Period: Draft

participants' medical records.

Payment: Veterans will receive \$20 per questionnaire related study contact (baseline, 2-month, 6-month) for a possible total of \$60.

b) Explain how the above research procedures are the least risky that can be performed consistent with sound research design.

Participation represents minimal risk for participants given that they will be told they can withdraw from the study at any time. Veterans will receive very basic information on behavioral weight management treatment options and questions do not differ substantially from what could be asked in usual care settings.

c) State if deception will be used. If so, provide the rationale and describe debriefing procedures. Since you will not be fully informing the participant in your consent process and form, complete an alteration of consent (in section 13). Submit a debriefing script (in section 16).

n/a

d) State if audio or video recording will occur. Describe what will become of the recording after use, e.g., shown at scientific meetings, erased. Describe the final disposition of the recordings.

We plan to record the 10-day phone call, which we may also transcribe. The primary use for these recordings is to assess treatment fidelity. However, de-identified written quotations may be used in manuscripts and presentations.

e) Describe alternative procedures or courses of treatment, if any, that might be advantageous to the participant. Describe potential risks and benefits associated with these. Any standard treatment that is being withheld must be disclosed in the consent process and form. (i.e. standard-of-care drug, different interventional procedure, no procedure or treatment, palliative care, other research studies).

n/a

f) Will it be possible to continue the more (most) appropriate therapy for the participant(s) after the conclusion of the study?

n/a

g) Study Endpoint. What are the guidelines or end points by which you can evaluate the different treatments (i.e. study drug, device, procedure) during the study? If one proves to be clearly more effective than another (or others) during the course of a study, will the study be terminated before the projected total participant population has been enrolled? When will the study end if no important differences are detected?

We plan to complete interim analyses at n=200. We propose using the conservative O'Brien-Fleming approach to determine whether the study should be stopped at the interim ($\alpha = 0.0054$ for the interim analysis and 0.0492 for the final analysis) as we do not expect to see effects at n=200. For futility at interim, we propose a conditional power approach where we stop for futility if the conditional power is below 10%.

If we do not see effects at interim, we will complete analyses of the primary outcome once we have 2-month follow-up data for the full sample. Analyses for secondary outcomes will be completed once the full sample completes the 6-month questionnaires.

3. Background

Title : The EMBER Trial for Weight Management Engagement

Approval Period: Draft

a) Describe past experimental and/or clinical findings leading to the formulation of the study.

As we have shown, almost 80% of veterans using the Veterans Health Administration (VHA) have overweight or obesity (1). While almost 95% are offered a weight loss treatments, only about 10% use one (2).

Motivational Interviewing is an empirically supported, patient-centered method for enhancing motivation by exploring and resolving ambivalence (3). While no self-help motivational interviewing tools exist for weight loss treatment engagement, there is support for self-help versions of motivational interviewing in other contexts (4-8). Therefore, we believe EMBER, a motivational, self-help tool could help engage veterans in weight loss treatments.

1. [name], J.Y., Phibbs, C. S., Hoggatt, K. J., Washington, D. L., Lee, J., Haskell, S., Uchendu, U. S., Saechao, F. S., Zephyrin, L. C., & Frayne, S. M. (2017). The Obesity Epidemic in the Veterans Health Administration: Prevalence among Key Populations of Women and Men Veterans. *Journal of General Internal Medicine*, 32(1): 11-17. doi: 10.1007/s11606-016-3962-1.

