Participants will be 470 VAPAHCS and Houston VAMC patients (235 at each site). Participants will have obesity as the goal of the tool is to engage such patients in weight loss treatments.

- b) State the age range, gender, and ethnic background of the participant population being recruited.

The veteran participant population will generally reflect the age and ethnicity of VA Palo Alto & Houston patients with obesity. We will oversample women to ensure their participation, given their low representation among VA users.

- c) State the number and rationale for involvement of potentially vulnerable subjects in the study (including children, pregnant women, economically and educationally disadvantaged, decisionally impaired, homeless people, employees and students). Specify the measures being taken to minimize the risks and the chance of harm to the potentially vulnerable subjects and the additional safeguards that have been included in the protocol to protect their rights and welfare.

Vulnerable subjects will be included in so far as they are representative of the patient population in VA. These individuals are likely to include individuals with mental health conditions. Because previous work tells us women veterans have a higher rate of mental health conditions than men veterans, it is important that we not exclude these vulnerable subjects. Also to the extent that they are represented in VA populations, participants may include employees, pregnant women, elderly, and economically disadvantaged individuals.

No children are included in this study, as it is a study of adult veterans.

- d) If women, minorities, or children are not included, a clear compelling rationale must be provided (e.g., disease does not occur in children, drug or device would interfere with normal growth and development, etc.).

Women and minorities are included. We will not include children as they do not receive care at VHA.

- e) State the number, if any, of participants who are laboratory personnel, employees, and/or students. They should render the same written informed consent. If payment is allowed, they should also receive it. Please see Stanford University policy.

We are not specifically recruiting employees or students.

Title : The EMBER Trial for Weight Management Engagement

Approval Period: Draft

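### The stated efficacy levels (0.0054 interim, 0.0492 final) have the O'Brien-Fleming shape of a half-way look, not of the planned look at 200 of 470, and under a two-sided 5% reading they spend slightly more than 5%

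*Protocol*

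**What the plan says.** The monitoring rule is in Protocol section 2g (Study Endpoint).

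- **Timing:** "We plan to complete interim analyses at n=200". One interim look is described.
- **Efficacy rule:** "We propose using the conservative O'Brien-Fleming approach to determine whether the study should be stopped at the interim", with alpha "0.0054$ for the interim analysis and 0.0492 for the final analysis".
- **Futility rule:** "we stop for futility if the conditional power is below 10" per cent. The text does not say whether this is binding, or under which effect the conditional power is computed.
- **Final analysis:** if the trial continues, "we will complete analyses of the primary outcome once we have 2-month follow-up data for the full sample".

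The full sample is 470. Section 1a says "In this two site study we will recruit patients (n=470", and section 8a and the Resources section give the same total. Section 2a fixes 1:1 allocation.

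The protocol states no overall alpha, sidedness, spending function or information fraction.

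**The concern.** An O'Brien-Fleming boundary depends on when the look is taken: the earlier the look, the stricter the interim level. The protocol names the method, the time of the look and both significance levels, so the three can be checked against each other, and they do not agree.

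The two levels decide whether the trial stops early for efficacy and whether the final result counts as significant. If the interim level is looser than the named method gives, an interim p-value between 0.0025 and 0.0054 would stop the trial at 200 participants where O'Brien-Fleming would continue. If the final level is not lowered to match, the overall error exceeds its target. Changing the levels after the interim data have been seen would be hard to defend, so any correction belongs before that look.

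**Working it through.** **Inputs.** Interim n = 200, interim level 0.0054 and final level 0.0492 (section 2g). Final n = 470 (sections 1a and 8a). Assumptions, because the protocol is silent: overall level 5% two-sided, futility non-binding, normal approximation.

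**Step 1: reproduce the stated pair.** The two-sided critical values are z(0.0054) = 2.782 and z(0.0492) = 1.967. Their ratio is 2.782/1.967 = 1.4145. In the O'Brien-Fleming form the final critical value is C and the interim one is C/√t, so the ratio is 1/√t. Setting 1/√t = 1.4145 gives t = 0.50. The pair is reproduced by C = 1.967 with t = 0.5, since 1.967 × √2 = 2.782. That is a look at 235 of 470.

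**Step 2: the planned look.** t = 200/470 = 0.4255, so the ratio should be 1/√0.4255 = 1.533.

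**Step 3: overall error of the stated pair.** Under the null, (Z1, Z2) is bivariate normal with correlation √t. The error is P(|Z1| > 2.782 or |Z2| > 1.967).

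- At t = 200/470 (correlation 0.652): 0.0518.
- At t = 0.5 (correlation 0.707): 0.0513.

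A simulation of 4 million draws at t = 200/470 gave 0.0519, in agreement. So C = 1.967 is slightly too small even for the half-way look that its shape fits.

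**Step 4: O'Brien-Fleming levels for an overall 5%.** Solve for C so that P(|Z1| > C/√t or |Z2| > C) = 0.05.

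| Look | C | Interim z | Interim p | Final p |
|---|---|---|---|---|
| 200/470 | 1.969 | 3.018 | 0.0025 | 0.0490 |
| 235/470 | 1.977 | 2.797 | 0.0052 | 0.0480 |
| Stated | 1.967 | 2.782 | 0.0054 | 0.0492 |

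Against the unrounded value at 200/470, the interim level is 0.0054/0.00254 = 2.1 times too large.

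**Step 5: other readings.** None returns the stated pair.

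- Lan-DeMets O'Brien-Fleming-type spending at 200/470 gives 0.0027/0.0489 (5% two-sided spending) or 0.0012/0.0496 (2.5% per side).
- Taken as one-sided levels against 5%, the stated pair totals 5.13% at 200/470. The one-sided O'Brien-Fleming pair is 0.0053/0.0479.
- A smaller final analysis set raises t. The two-sided total stays above 5% until t is about 0.70, that is 200/0.70 ≈ 286 analysed at the end. The protocol plans for the full sample.

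**Step 6: one level held fixed.** Keeping 0.0054 at the interim and solving for a total of 5% at 200/470 gives a final level of 0.0474. Keeping 0.0492 at the end gives an interim level of 0.0021.

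**Step 7: power.** The protocol gives no effect size, so assume a drift that yields 80% or 90% for a fixed two-sided 5% test: 1.960 + 0.842 = 2.802, or 1.960 + 1.282 = 3.242. Power with the stated pair is 80.01% and 89.99%. With 0.0025/0.0490 it is 79.84% and 89.89%, a loss of 0.17 and 0.10 points.

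**The case against.** **The futility rule.** If it were binding, the total two-sided error at 200/470 would fall below 5%: 4.5% (current trend, applied symmetrically), 2.5% (current trend, one direction), and 3.4% or 3.8% (conditional power under an assumed 80% or 90% design effect). This stands as a limit on the claim. The protocol does not say that the rule is binding, and efficacy levels are normally set without relying on it. The 5.18% must still carry that condition.

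**The 5% target.** The protocol does not state it. Under one-sided 5% the interim level is nearly right (0.0053), and only the final level (0.0479 against 0.0492) is too high.

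**Practical size.** The primary outcome is binary (section 2a), and the background section puts treatment use at about 10%. With that rate assumed in both arms and 100 then 235 per arm, the stated pair with an uncorrected chi-square test gives 5.0–5.1% in simulation, about what a single test at 0.05 gives. With Fisher's exact test it gives 3.6%. So whether the real error passes 5% depends on the test, which may be left to the SAP. This supports calling the excess negligible. It does not make the pair the O'Brien-Fleming one.

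**Stronger readings that a reader might infer.**

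- *That the trial fails to control type I error in any material sense.* The documents do not support this: the excess is 0.18 points and conditional on non-binding futility.
- *That the interim bar demands half the evidence it should.* The factor of two is a ratio of small p-values. On the z scale it is 2.78 against 3.02, and p < 0.0054 is still demanding.
- *That n=200 counts enrolments, so the true fraction is lower still.* The interim tests a 2-month outcome taken from VA records, so 200 participants with that outcome is the natural reading. The exact data cut is a detail that a SAP may settle.

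**Conclusion.** The point holds as an inconsistency between the named method, the planned timing and the stated levels. The pair fits a look at 235 of 470, whereas the plan looks at 200 of 470, and no reading tried reproduces it.

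The size of the error excess rests on three assumptions that the protocol leaves open: overall 5%, two-sided, futility non-binding. Under these the excess is real but small. The mismatch at the interim matters more than the excess, because section 2g calls the approach conservative while setting an interim level looser than that approach gives for this look.

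This is a correction to make before the interim data are unblinded. It is not a threat to the validity of the trial.

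**What to change.** In section 2g:

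1. State the overall alpha and whether it is two-sided.
2. Replace the pair with the levels for 200/470, which are 0.0025 and 0.0490 for classical O'Brien-Fleming at two-sided 5%. Alternatively, name an O'Brien-Fleming-type spending function and evaluate it at the actual information fraction.
3. If 0.0054 is to be kept at the interim, lower the final level to 0.0474.

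The change is two numbers and one sentence. Moving to 0.0025/0.0490 loses about 0.1 to 0.2 points of power under the assumed 80–90% design. Keeping 0.0054 with 0.0474 costs somewhat more: the same calculation gives 79.56% and 89.71%, a loss of about 0.4 and 0.3 points. The recruitment target need not change.
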